#### 4.1.2.2 TIME TO DC, CR, CRMIN AND CROFF

Time to reaching DC, CR, CRmin and CRoff in each treatment period and in the follow-up phase will be derived as described below and will be analyzed overall and by subgroup of disease status at roll-over.

Time to attaining a disease status X within a treatment period, will be calculated as the difference between the first date that status X was achieved and the first IMP administration date in that treatment period.

Participants without any disease assessment in the treatment period are censored at day 1. Participants with disease assessment but not achieving status X during the treatment period are censored at the end of the treatment period.

Time to disease status X (days) =

date (first date of achieving status X/end of treatment period) - first IMP administration date in the treatment period + 1

Time to status X for a specific treatment period will only be calculated in case the participant can still reach that status within the treatment period.

This means that for the roll-over phase of participants who enter study 1905 on CRmin, only the time to CRoff will be calculated. This will be done by replacing the first IMP administration date in the formula presented above with the date of the roll-over visit.

Time to attaining a disease status X within treatment period 1 or the follow-up phase will be calculated in case the participant can still reach that status in treatment period 1 or the follow-up phase respectively.

Time to disease status X (days) within the follow-up phase=

date (first date of achieving status X/end of follow-up phase) – start date of follow-up phase +1

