- flare between DC and achieving CRmin that is not controlled by 2 dose levels of OCS above the dose at which the flare is observed and that is at least 0.3 mg/kg/day (Table 4)

In the absence of DC, participants will receive prednisone at the starting dose of 1.5 mg/kg/day. In case of uncontrolled flare before CRmin, participants will receive, as starting dose, the last dose from ARGX-113-1904. In case of flare after CRmin, participants will receive a prednisone dose in line with the severity of the flare, with the recommendation of a minimum of 0.3 mg/kg/day when the flare is of mild severity (PDAI activity score <15) and of 0.5 mg/kg/day when the flare is moderate to severe (PDAI activity score \geq 15). Dosing of efgartigimod PH20 SC will be done during on-site visits or home visits according to Table 2.

5. Participants who developed a prednisone-related SAE may prematurely roll over into ARGX-113-1905 and may be treated with efgartigimod PH20 SC through on-site or home visits according to the clinical statuses as described above. Concomitant prednisone will be considered to fit the clinical statuses as described above as far as compatible with the nature and severity of the SAE, with a lower dose to no concomitant prednisone being considered otherwise.

Participants or their caregivers (a person of legal age that the participant proposes to perform the administrations) may self-administer efgartigimod PH20 SC after they have successfully completed self-administration training (in ARGX-113-1904 with at least 1 refresher training in OLE trial ARGX-113-1905, or during ARGX-113-1905). All participants and/or their caregivers will receive a home guide for transport, storage, preparation, and administration of the IMP.

At any postbaseline visit before DC is achieved, the prednisone dose will be adjusted by incrementing dosage according to clinical judgment, with the recommendation to increase by 1 or more steps (Table 4) in case of disease progression or insufficient clinical change. To facilitate common judgments among investigators, recommendations for assessment of disease progression and insufficient clinical change are:

- Disease progression: increase of at least 5 in PDAI activity score compared to baseline score, observed at any postbaseline visit before DC

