- Insufficient clinical change: the absence of DC after 3 to 4 weeks of the participant being treated at the starting baseline prednisone dose or after 3 to 4 weeks of any new incremented dose of prednisone

The recommendations of the prednisone dose escalation are:

- Stepwise escalation of daily prednisone dose by 1 or more steps according to clinical judgment in case of disease progression
- Adjustment by incrementing dosage by 1 step in case of insufficient clinical change
- Possible further escalation from the previous step by 1 or more steps, according to clinical judgment and under the same recommendation as above
- Maximum escalation to 1.5 mg/kg qd for 3 weeks

If DC is not attained after a minimum of 3 weeks of the participant receiving oral prednisone 1.5 mg/kg qd, then the participant will be considered a treatment failure and will be withdrawn from the trial.

For participants who achieve DC at the starting dose of 0.5 mg/kg qd or lower, the prednisone dose will be maintained at that starting dose qd until CR and 2 weeks thereafter, or EoC and 4 weeks thereafter, after which tapering will be initiated. For participants achieving DC with an escalated prednisone dose (ie, >0.5 mg/kg qd), that dose will be maintained until 2 weeks after achieving DC and then will be tapered (Table 4) in increments of 0.25 mg/kg every 2 weeks until the starting dose is achieved. This starting dose will be maintained until a sustained CR is achieved for 2 weeks, after which further tapering will be initiated, or prednisone tapering below 0.5 mg/kg qd may be initiated in case of sustained EoC for 4 weeks. Further tapering will be performed thereafter, as long as CR or EoC are sustained. Each new tapered prednisone dose until 20 mg/day must be maintained for 2 weeks. Then, the prednisone dose is further tapered by 2.5 mg/day per week. When 10 mg/day is reached, this dose level will be maintained for at least 8 weeks until CRmin is achieved. The prednisone dose can then be further tapered to reach CRoff according to the clinical judgment of the investigator.

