- flare between DC and achieving CRmin that is not controlled by 2 dose levels of OCS above the dose at which the flare is observed and that is at least 0.3 mg/kg/day

In the absence of DC, participants will receive prednisone at the starting dose of 1.5 mg/kg/day. In case of uncontrolled flare before CRmin, participants will receive, as starting dose, the last dose from 1904. In case of flare after CRmin, participants will receive a prednisone dose in line with the severity of the flare.

• Participants who developed a prednisone-related SAE may prematurely roll over into 1905 and may be treated with EFG PH20 SC through onsite or home visits according to the clinical statuses as described above. Concomitant prednisone will be considered to fit the clinical statuses as far as compatible with the nature and severity of the SAE, with a lower dose to no concomitant prednisone being considered otherwise.

Details on the rules for prednisone dose adjustment can be found in the clinical trial protocol (CTP).

SGS	Statistical Analysis Plan	
ARGX-113-1905	Final analysis	Final 1.0 of 26APR2024

If DC is not attained after a minimum of 3 weeks of the participant receiving oral prednisone 1.5 mg/kg qd, then the participant will be considered a treatment failure and will be withdrawn from the study.

In case of flare in the period between DC and CRmin, the prednisone dose will be increased to achieve DC again. Participants who are not controlled by a dose that is 2 dose levels above the dose at which the flare is observed and that is at least 0.3 mg/kg/day, will be managed according to clinical judgment ie, either receive a further increased prednisone dose or be withdrawn from the study. Withdrawal of participants with a flare before CRmin will be defined as treatment failure.

In case of flare after having achieved CRmin (ie, while being off treatment with EFG PH20 SC), participants will be immediately treated/re-treated with EFG PH20 SC. The first day of new EFG PH20 SC treatment will define a new baseline for assessments of outcomes (DC, CR, etc.) and prednisone escalation or tapering schedule.

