#### Table 1: Phase, period and subperiod definition

Document template OTH.STAT.010 v3

CONFIDENTIAL AND PROPRIETARY

System Version: 1.0, Status: Approved, Document ID: VV-TMF-172580

SGS	Statistical Analysis Plan	
ARGX-113-1905	Final analysis	Final 1.0 of 26APR2024

Treatment period 1 is only applicable for participants who did not achieve CRmin or CRoff in 1904

Treatment	Treatment period 1 b,c	On-treatment 1	Earliest of (date of signing the informed consent form (ICF) of study 1905 and date of roll-over), with 00:00 added as time part a .	For the participants with off- treatment 1 subperiod : last IMP administration date/time in treatment period 1. For other participants: Date of week 52/EoT/ET visit, with 23:59 added as time part.
			1	For participants who don't have a week 52/EoT/ET visit: date of last contact, with 23:59 added as time part.
		Off-treatment 1	administration date/time in treatment period 1	For the participants with a next treatment period: first IMP administration date/time in next treatment period – 1 minute.
			+ 1 minute	For other participants:
			Date of week 52/EoT/ET visit, with 23:59 added as time part.	
			For participants who don't have a week 52/EoT/ET visit: date of last contact, with 23:59 added as time part.	
	Treatment n	eriod 2 is applicab	le for participants with	flare after CRmin in the roll-over

Treatment period 2 is applicable for participants with flare after CRmin in the roll-over phase or in treatment period 1 and who re-initiate IMP administration

Treatment period 2 °	On-treatment 2	First IMP administration date/time in treatment period 2	For the participants with off- treatment 2 subperiod : last IMP administration date/time in treatment period 2.
			For other participants:
			Date of week 52/EoT/ET visit, with 23:59 added as time part.
			For participants who don't have a week 52/EoT/ET visit: date of last contact, with 23:59 added as time part.

Page 18 of 84

SGS	Statistica	al Analysis Plan		
ARGX-113-1905	F	inal analysis		Final 1.0 of 26APR2024
	Off-treatment 2	Last IMP administration date/time in treatment period 2	trea adm	the participants with a next tment period: first IMP ninistration date/time in next tment period – 1 minute.
		+ 1 minute For	For	other participants:
				e of week 52/EoT/ET visit, h 23:59 added as time part.
			wee last	participants who don't have a ek 52/EoT/ET visit: date of contact, with 23:59 added as e part.
Etc c				

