#### 4.1.3.2 TIME TO DC, CR, CRMIN AND CROFF

Time to DC, Time to CR, Time to CRmin and Time to CRoff will be descriptively presented with median times, quantiles and number and percentage of participants censored and with event, as obtained through Kaplan-Meier analysis.

The tables will be produced for PV participants and for all participants (PV+PF), also overall and by disease status at roll-over.

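### Treatment-failure withdrawals are censored when they leave, so Kaplan-Meier medians and quantiles for time to CR, CRmin and CRoff can only be right or too early

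*SAP*

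**What the plan says.** - **Censoring.** SAP 4.1.2.2: "Participants with disease assessment but not achieving status X during the treatment period are censored at the end of the treatment period". No exception is made for treatment failure.
- **End of the period.** For a participant with no off-treatment subperiod or later treatment period, SAP Table 1 gives "Date of week 52/EoT/ET visit, with 23:59 added as time part", or last contact if there is no such visit. Protocol 7.2 places the early-termination visit at withdrawal.
- **Withdrawal for failure.** If DC is absent after at least 3 weeks on 1.5 mg/kg, SAP 1.2 says "then the participant will be considered a treatment failure and will be withdrawn from the study". For an uncontrolled flare before CRmin, the participant may "either receive a further increased prednisone dose or be withdrawn from the study", and withdrawal then counts as treatment failure.
- **Estimator.** SAP 4.1.3.2 reports medians, quantiles, and numbers censored and with event, "as obtained through Kaplan-Meier analysis". SAP 8.1 lists these as topline tables, overall and by disease status at roll-over.
- **The same participants elsewhere.** SAP 4.1.2.1 counts a participant never recorded as CRmin as a non-responder. SAP 4.1.2.6 and 4.1.3.6 tabulate treatment failures separately.

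**The concern.** Kaplan-Meier assumes that a censored participant has the same future chance of the event as those still under observation. Here the opposite is built in: under both failure routes, lack or loss of response leads to the withdrawal and so to the censoring. The estimate then describes how fast response would come if failures went on to respond like everyone else.

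The SAP also treats the same people in two ways, as non-responders in the CRmin proportion and as censored in time to CRmin. The treatment-failure table does not repair this, because a reader cannot recover the right median from a proportion. At stake are topline medians that could make efgartigimod look faster than it was in the participants who entered, most of all in roll-over groups where failure is likeliest.

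**Working it through.** There is no planned figure to reproduce: the trial has no hypothesis, sample-size calculation or expected median.

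**1. Direction.** Suppose a share f of participants fails before the first event, and F(t) is the proportion of non-failures who have responded by time t.

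- Failures censored: 1 − KM = F(t).
- Failures kept at risk: proportion responding = (1 − f) × F(t).

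When the planned curve reaches 50%, the proportion that has actually responded is 0.5 × (1 − f): 47.5, 45, 40 and 35% for f = 5, 10, 20 and 30%. This holds whatever the response rate or shape. If failures and events overlap in time, keeping failures at risk still only enlarges the risk sets, so the planned quantile is never later than the corrected one.

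**2. Timing from the documents** (Protocol 4.1 and Table 4).

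*Mandated failure.* Protocol 4.1: "In the absence of DC, participants will receive prednisone at the starting dose of 1.5 mg/kg/day". The ceiling is "Maximum escalation to 1.5 mg/kg qd for 3 weeks", so a participant starting there can fail from week 3. With single-step escalation every 3 to 4 weeks:
- from 0.5 mg/kg: 4 steps × 3 to 4 weeks + 3 = weeks 15 to 19
- from 0.3 mg/kg: 5 steps × 3 to 4 weeks + 3 = weeks 18 to 23

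*Earliest CRmin.* Protocol 4.1: "When 10 mg/day is reached, this dose level will be maintained for at least 8 weeks until CRmin is achieved". Take DC or CR at week 1, the shortest step durations, and body weight up to about 77 kg:
- from 1.5 mg/kg: 1 + 8 (1.5, 1.25, 1.0 and 0.75 mg/kg, 2 weeks each) + 2 (0.5 mg/kg) + 2 (20 mg) + 3 (17.5, 15, 12.5 mg) + 8 (10 mg) = week 24
- from 0.5 mg/kg: 1 + 2 + 2 + 3 + 8 = week 16
- from 20 mg: 1 + 2 + 3 + 8 = week 14

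Among those starting at 1.5 mg/kg, mandated failures can therefore leave well before any CRmin event. CRoff needs a further 8 weeks without prednisone, so its events come later still.

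**3. Illustrative size for CRmin.** Assumptions: 75% of non-failures respond, evenly over weeks 14 to 51; failures withdrawn evenly over weeks 3 to 23; 400,000 simulated participants per scenario.

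| Failures | Planned median (weeks) | Failures kept at risk (weeks) | Too early (days) | Crude % with event, both rules |
|---|---|---|---|---|
| 5% | 38.8 | 40.0 | 9 | 71 |
| 10% | 38.8 | 41.4 | 18 | 68 |
| 20% | 38.9 | 44.8 | 41 | 60 |
| 30% | 39.1 | 49.2 | about 70 | 53 |

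Hand check at 20%, treating all failures as leaving before week 14:
- planned: 14 + 37 × 0.5/0.75 = 38.7 weeks
- corrected: 14 + 37 × 0.5/(0.75 × 0.8) = 44.8 weeks

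The planned median barely moves as failures rise from 5% to 30%.

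If only 60% of non-failures respond, the planned median is about 14 + 37 × 0.5/0.6 = 44.8 weeks. The true proportion responding peaks at 0.8 × 60 = 48% or 0.7 × 60 = 42% for 20 or 30% failures, so the median is in fact not reached.

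**4. CR and DC.**
- CR, assuming lognormal times with median 8 weeks and sigma 0.6, failures at weeks 3 to 15: the median moves by 0 to 1 week for 5 to 30% failures. The upper quartile is 13 v 13, 14 v 15, 15 v 21, and 16 weeks v not reached.
- DC, assuming lognormal times with median 21 days: a mandated failure cannot be censored before about day 22, and the medians agree within 0.1 day at every failure rate. The 75th percentile is 33.9 v 34.0, 37.3 v 37.6, 49.3 v 52.6, and 161.8 days v not reached.

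**The case against.** The strongest reply is about consequence. Efficacy is secondary and descriptive, with no test. The time tables print numbers censored, the CRmin and CRoff proportions count failures as non-response, and failures are tabulated with reasons by roll-over status. At 5 to 10% failures the CRmin shift is 9 to 18 days, against on-site assessment every 4 weeks between CR and CRmin. With 100 participants and 10% failures, the simulated 95% sampling range of the median is about 34 to 44 weeks, against a bias of 2.6 weeks. The largest shifts need 30% failures, which nothing in the documents supports. All of this stands, and it keeps the point from being critical. But a systematic error in one direction is not excused by sampling noise, and a topline median should still describe the participants.

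Exposure also differs by group. Participants entering in CR or DC can essentially fail in period 1 only through a flare, where withdrawal is discretionary. Some may reach CRmin before week 14, because their 8 weeks at 10 mg can begin in ARGX-113-1904. The main scenario pools groups with different timing, so the result in which all failures precede the first event fits the 1.5 mg/kg starters, not the overall table. Group-specific and mixed versions nevertheless gave similar shifts: about 7 to 11, 14 to 25 and 32 to 59 days at 5, 10 and 20% failures.

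Finally, the SAP definition of treatment failure includes absence of DC due to a prednisone-related SAE, which is not withdrawal for poor response alone. The revised rule should say how these are handled.

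**Conclusion.** The concern holds. The censoring is informative by design, nothing else in the SAP corrects it, and the direction follows by algebra. The size is conditional: nil without failures, small for the CR median at modest failure rates, negligible for the DC median, and potentially weeks for CRmin. No CRoff figure was calculated; the same direction applies. Under the assumed 75% response, the CRmin median is 9 to about 70 days too early for 5 to 30% failures. With 60% response and 20% or more failures, a median of about 45 weeks would be printed when it is not reached. Failure rates, response rates and response-time shapes are all assumptions. The proportions, the percentage with event and the primary safety analysis are unaffected. This should be changed, but it does not threaten the trial's main conclusions.

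**What to change.** In SAP 4.1.2.2, state that a participant withdrawn as an investigator-assessed treatment failure without reaching status X stays at risk as a non-responder until the date planned for study week 52. This remains Kaplan-Meier, as Protocol 9.5.6 specifies. Alternatively, take the median and quantiles from the Aalen-Johansen cumulative incidence with treatment failure as the competing event.

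Say explicitly that the SAE-related failure category is included; that is the simplest choice and matches the non-response rule in SAP 4.1.2.1. Keep administrative and unrelated-withdrawal censoring as it is, and show the current analysis as a sensitivity analysis. Treating retreatment for flare as a competing event for CRoff is optional, because these times are defined within each treatment period.

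The cost is one rule and minor programming on data already collected. Some medians will lengthen or be reported as not reached.

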#### Table 3: Analysis visits

Document template OTH.STAT.010 v3

Page 21 of 84

System Version: 1.0, Status: Approved, Document ID: VV-TMF-172580

SGS Statistical Analysis Plan				
ARGX-113-1905		Final	analysis	Final 1.0 of 26APR2024
	Week 51	358	355	361
	Week 52	365	362	End day of phase
Follow-up	FU Week 4	28	1	42
	FU Week 8	56	43	End day of phase

a Baseline is the assessment at the roll-over visit, so no analysis visit windows are required for this time point. For participants with a roll-over phase, the baseline analysis visit will be assigned to the roll-over phase and will not be repeated in the treatment phase. For participants without a roll-over phase, the baseline analysis visit will be assigned to the treatment phase.

b x=1,..., 10 for roll-over phase, x=1,...,.47 for treatment phase

An assessment at the roll-over visit will be attributed to Baseline in case it is before the first IMP administration, to Week 1 otherwise.

Baseline is defined in section 2.2.2.

For the analysis of ECG, a 12-weekly allocation will be used, as defined in Table 4.

Phase	Analysis window	Target ADYP	Lower limit ADYP	Upper limit ADYP
Treatment	Baseline a	-	-	-
	Week 12	85	1 a	127
	Week 24	169	128	211
	Week 36	253	212	295
	Week 48	337	296	361
	Week 52	365	362	End day of phase
Follow-up	FU Week 4	28	1	42
	FU Week 8	56	43	End day of phase

Table 4: Analysis visits for ECG

a Baseline is the assessment at the roll-over visit, so no analysis visit windows are required for this time point.

x=1 through the maximum number of 12-weeks periods on treatment for any participant minus 2

For GTI wider windows are used:

- Week 26 (wide range): from ADY=145 until ADY=221 with target on ADY=183
- Week 52 (wide range): from ADY=327 until ADY= end of treatment phase with target on ADY=365
- Other assessments will be allocated as in table 3 but will not be presented in the tables (only in listings).
- Additional visit window: Endpoint: last record post baseline.

_	SGS	Statistical Analysis Plan	
AF	GX-113-1905	Final analysis	Final 1.0 of 26APR2024

Analysis of ABQOL and EQ-5D-5L will be done on following visits:

- Roll-over (per CRF visit)
- At CRmin (assessment done within 28 days after achieving CRmin)
- At start of new treatment period
- At EoT/ET (per CRF visit)

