#### 4.1.2.5 TIME TO FLARE AFTER CRMIN

For participants who achieve CRmin (in 1904 or 1905) in a treatment period or in the follow-up phase, time to flare after CRmin will be calculated as:

(visit date of flare) - (date of CRmin) + 1.

Participants who do not experience a flare are censored at the end of the treatment period (or roll-over or follow-up phase as applicable).

For the roll-over phase of participants who enter study 1905 on CRmin, use date of roll-over visit instead of date of CRmin.

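### Without an end visit, and in the tail of the follow-up phase, time-to-event endpoints are censored at an undefined date of last contact, so unassessed time can count as event-free

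*SAP*

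**What the plan says.** SAP 4.1.2.2 gives two censoring rules for time to DC, CR, CRmin and CRoff within a treatment period. The first is "Participants with disease assessment but not achieving status X during the treatment period are censored at the end of the treatment period". The other rule is "Participants without any disease assessment in the treatment period are censored at day 1". For the follow-up phase the formula is "date (first date of achieving status X/end of follow-up phase) – start date of follow-up phase +1", so a participant without the status runs to the end of that phase. For flare after CRmin, SAP 4.1.2.5 says "Participants who do not experience a flare are censored at the end of the treatment period (or roll-over or follow-up phase as applicable".

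The end dates come from SAP 2.2.1, Table 1. If a new treatment period follows, the period ends one minute before its first dose. Otherwise it ends at the week 52/EoT/ET visit, with this fallback: "For participants who don't have a week 52/EoT/ET visit: date of last contact, with 23:59 added as time part". The roll-over phase of participants never treated with IMP has the same fallback. The follow-up phase ends at last contact for everyone. Neither document defines the date of last contact.

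Treatment period 1 opens at "Earliest of (date of signing the informed consent form (ICF) of study 1905 and date of roll-over), with 00:00 added as time part". Under Table 3, "For participants without a roll-over phase, the baseline analysis visit will be assigned to the treatment phase". Both schedules of activities mark a disease assessment at the roll-over visit, at the week 52/EoT/ET visit and at both follow-up visits.

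The results are Kaplan-Meier medians, quantiles and counts (SAP 4.1.3.2 and 4.1.3.5). SAP 4.1.2 says these endpoints use all measurements, not only the one nearest each target day. No sensitivity analysis of the censoring date is planned.

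**The concern.** Whether a participant has DC, CR, CRmin, CRoff or a flare is established by disease assessment. If the last assessment is at week 20 and the last contact is at week 30, weeks 20 to 30 tell us nothing about the event unless that contact recorded disease status. The SAP rule nevertheless keeps the participant in the Kaplan-Meier risk set for those ten weeks as event-free. The denominators are then too large, so estimated event probabilities fall and times lengthen.

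The direction matters. For DC, CR, CRmin and CRoff the distortion makes the drug look slower, which is conservative. For flare after CRmin it makes remission look more durable, which favours the product.

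The day-1 rule shows that the SAP does not intend participants with no assessment to accrue event-free time. In period 1 that intention can fail: the predose roll-over assessment can fall inside the period, and the rule does not require a post-baseline assessment.

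**Working it through.** **1. Who is affected.** Set the rules beside the schedules.

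- End visit held: a disease assessment is scheduled at it, so period end and last assessment normally coincide.
- Retreatment follows: the period ends just before the new first dose, close to the assessment that confirmed the flare.
- No end visit: the period, or the untreated roll-over phase, ends at last contact, and a gap is possible. Protocol 7.2 asks for the early termination visit only where feasible and lets the participant decline it; protocol 7.3 provides for loss to follow-up.
- Follow-up phase: it always ends at last contact, so a gap is possible after the last follow-up assessment.

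**2. Day-1 rule in period 1.** Take a participant first dosed on day 1, assessed only at roll-over, with no end visit and last contact on day 120. If the roll-over assessment counts as being in the period, the SAP formula gives 120 − 1 + 1 = 120 event-free days. The day-1 rule would have given 1 day. From period 2 on, the period starts at the first dose, so a predose assessment lies outside it and the rule can operate.

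**3. Hand example.** Ten participants: flares at weeks 8, 16, 24, 32 and 40; two last assessed at week 4 with last contact at week 30; three complete to week 52. Take the median as the first time the curve is at or below 50%.

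- SAP rule: survival at week 26 is 9/10 × 8/9 × 7/8 = 0.700, so flare is 30.0%. Five are then at risk at week 32: 0.700 × 4/5 × 3/4 = 0.420, so flare at week 52 is 58.0%. The median is week 40.
- Last assessment: survival at week 26 is 7/8 × 6/7 × 5/6 = 0.625, so flare is 37.5%. Then 0.625 × 4/5 = 0.500 at week 32, and × 3/4 = 0.375, so flare at week 52 is 62.5%. The median is week 32, where the curve touches exactly 50%.

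The example is deliberately small and shows what two such participants can do in a subgroup.

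**4. Size in a large sample.** The plan states no figure for these endpoints, so there is none to reproduce. Illustrative event rates come from the prednisone study cited in protocol 2.2: 45% flare within 6 months and 64% CRmin after 12 months. With exponential times, the weekly rates are −ln(0.55)/26 = 0.0230 and −ln(0.36)/52 = 0.0196. True week-52 probabilities are 1 − 0.55² = 69.8% and 64.0%. The share lost without an end visit and the gap from last assessment to last contact are assumptions; neither document gives them. The simulation used 400,000 participants per scenario, 4-weekly assessments and loss uniform over 52 weeks. Week-52 Kaplan-Meier estimates (SAP rule / last assessment):

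| Loss | Gap (weeks) | Flare, % | CRmin, % |
|---|---|---|---|
| 5% | 8 | 69.5 / 69.8 | 63.8 / 64.1 |
| 10% | 8 | 69.1 / 69.7 | 63.5 / 64.1 |
| 10% | 26 | 67.8 / 69.7 | 62.3 / 64.1 |
| 20% | 8 | 68.5 / 69.8 | 62.6 / 63.9 |
| 20% | 26 | 66.0 / 69.8 | 60.4 / 64.1 |
| 30% | 26 | 63.8 / 69.7 | 58.1 / 63.8 |

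With a 2-week gap, shorter than the visit interval, the two rules agree. Median time to flare stays at 32 weeks except with a 26-week gap at 20% or 30% loss, where the SAP rule gives 36. Median time to CRmin is 36 weeks when censored at last assessment. Under the SAP rule it is 36 at 10% loss with an 8-week gap, 40 at 20% with 8 weeks, and 44 at 30% with 26 weeks.

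**The case against.** Several points on the other side stand.

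The affected group is narrow, as step 1 shows. Protocol 7.1 also has early discontinuers complete the end-of-treatment assessments and 8 weeks of follow-up. A reader might infer that the Kaplan-Meier summaries of all five endpoints are biased throughout. The documents do not support that: for participants with an end visit or retreatment, the two censoring dates nearly coincide.

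A reader might also infer that all time after the last visit is unobserved. Some contacts do capture disease status. Protocol section 8 has the investigator telephone home-treated participants every 2 weeks to confirm CR and ask about new lesions, and Appendix 11 allows DC, CR and flare to be assessed by telephone. Participants who suspect new lesions are asked to come in. However, the two-weekly calls run only until CRmin, so they do not cover the interval for flare after CRmin. Nothing requires the date of last contact to be such a call.

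A third tempting reading is that the day-1 rule can never operate in period 1. That assumes the roll-over assessment was done and is counted as a period 1 assessment. The visit is also the end visit of ARGX-113-1904, and SAP 2.2.3 describes baseline as the last available value from that study. The rule could still operate if the assessment is missing or held only as data from that study. What stands is that the wording leaves the matter open.

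Finally, the effect is modest beside sampling error. Even if all 213 possible participants (SAP 1.3) contributed, the binomial standard error for a 45% flare probability would be √(0.45 × 0.55/213) = 3.4 percentage points. No hypothesis is tested (protocol 9.2), so no error rate is at stake.

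**Conclusion.** The point holds in a limited form. As written, the SAP can credit unassessed time as event-free for participants without an end visit and at the end of the follow-up phase, and it does not make the day-1 rule secure in period 1.

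On the illustrative event rates, the simulated week-52 probability falls by 0.6 points at 10% loss with an 8-week gap, 1.3 points at 20% with 8 weeks, and 5.9 points for flare (5.7 for CRmin) at 30% with 26 weeks. These sizes rest on assumed loss and gaps, constant event rates and 4-weekly assessment. Neither document shows whether loss would differ by prior arm or entry status, so no between-group distortion can be claimed. Subgroup tables are where a few participants could matter: 213 participants split evenly over two prior arms and five entry statuses would be about 21 per cell.

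The change is worth making because time to flare errs in the product's favour and the correction is almost free.

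**What to change.** In SAP 4.1.2.2, censor participants without the event at their last disease assessment within the treatment period or phase, counting documented remote disease assessments. Censor at day 1 if there is none after the first IMP administration of that period, or after the start date for the roll-over and follow-up phases.

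In SAP 4.1.2.5 the clock starts at CRmin, so a day-1 rule tied to first IMP would not fit. Censor at the last disease assessment on or after CRmin (on or after the roll-over visit for the roll-over phase) within the period or phase. Censor at day 1 counted from that origin if there is no later assessment.

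Record the change in SAP 6.3. It takes a few sentences of text and some reprogramming of the censoring date. Disease assessments are already collected, and disease status and flares are listed (Listing 16.2.6.1). The downside is slightly shorter follow-up for a few participants.
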